### 6.4 Risks and Benefits

The inclusion and exclusion criteria are selected to enroll subjects with CU most likely to benefit from participating in the study. The overall risk will be minimized by compliance with the inclusion/exclusion criteria, close clinical monitoring including the use of a diary to monitor symptoms, and the use of rescue medication. See the Investigator Brochure for the complete safety summary of AK002.

The long-term continuation treatment will provide the option of an additional 12 months of treatment for patients with severe disease at baseline who recorded a complete response while on treatment with AK002 (1 mg/kg or 3 mg/kg) and who developed severe symptoms within 6 months of discontinuing AK002. The continuation protocol will be limited to patients who have no other treatment options, that is CholU, UF, or Xolair failures in patients with CSU.

The Investigator will provide the patient with written instructions to contact them if symptoms of CU worsen. Investigators will be instructed on acceptable treatments for worsening CU, which will allow subjects to continue on the study. The clinical benefits and safety profile of AK002 in subjects with CU has not yet been established. The risk for subjects participating in this study includes the potential for known safety issues, such as hypersensitivity reactions including anaphylaxis (Appendix 1), as well as for any unknown safety effects that could occur.

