### **7.2.2 Exclusion Criteria**

- 1) Acute urticaria
- 2) Concurrent/ongoing treatment with immunosuppressives (e.g., cyclosporine, methotrexate, dapsone, or others) within 4 weeks or 5 half-lives prior to Baseline, whichever is longer
- 3) Significant medical condition rendering the patient immunocompromised or not suitable for a clinical trial
- 4) Significant concomitant illness that would adversely affect the subject's participation or evaluation in this study
- 5) History of malignancies within five years prior to screening other than a successfully treated non-metastatic cutaneous, basal, or squamous cell carcinoma and/or in situ cancer
- 6) Presence of clinically significant laboratory abnormalities
- 7) Lactating women or pregnant women
- 8) Substance abuse (drug or alcohol) or any other factor (e.g., serious psychiatric condition) within the last 5 years that could limit the subject's ability to comply with study procedures
- 9) Subjects who are detained officially or legally to an official institute or those that have been committed to an institution by virtue of an order issued either by the judicial or the administrative authorities will be excluded
- 10) Use of omalizumab within the last 2 months
- 11) Receipt of intravenous IgG therapy 30 days prior to Baseline
- 12) Plasmapheresis 30 days prior to Baseline
- 13) Use (daily or every other day) of Doxepin 14 days prior to Baseline
- 14) Receipt of inactive vaccination or live attenuated vaccine 30 days prior to Baseline
- 15) Use of H2-antihistamines 7 days before Baseline

- 16) Intake of leukotriene antagonists within 7 days prior to enrollment
- 17) Intake of systemic corticosteroids (e.g., oral or depot) within 14 days prior to enrollment
- 18) Positive screening for ova and parasite test at Baseline
- 19) Treatment of helminthic parasite within 6 months of screening
- 20) Positive HIV serology at screening
- 21) Positive Hepatitis serology at baseline, except for vaccinated patients or patients with past but resolved hepatitis at screening
- 22) Donation or loss of >500 mL of blood within 56 days prior to administration of study drug or donation of plasma within 7 days prior to administration of drug
- 23) Known hypersensitivity to any ingredients of AK002 or drugs related to AK002 (e.g., monoclonal antibodies, polyclonal gammaglobulin)

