### **8.2 Concomitant Treatment**

One hour prior to dosing with AK002, subjects will receive pre-treatment oral doses of acetaminophen/paracetamol (1000 mg) and cetirizine (10 mg) for doses 1 and 2. Any premedication for subsequent doses will be based on the Investigator's discretion.

Subjects will be treated with a standard dose of second-generation AH (once per day) or up to a 4-fold dose of second-generation AH (standard of care) with dose and regimen established during Screening. In the event of symptom resolution during the study, the dose and schedule of AH treatment established during screening must be continued throughout the study.

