### 8.3.5 AK002 Administration

Premedication with oral doses of acetaminophen/paracetamol (1000 mg) and cetirizine (10 mg) will be given 1 hour prior to the infusion for doses 1 and 2. Any premedication for subsequent doses will be based on the Investigator's discretion. AK002 will be infused through a peripheral vein IV set. The IV line will be kept open before and after the infusion with sufficient quantities of 0.9% NaCl to assure patency.

Based on the patient's weight, the designated clinical staff will prepare the appropriate dilution of AK002 at 0.3 mg/kg (for Day 1), 1 mg/kg (for Day 29 and Day 57), and 3 mg/kg (for Day 85, Day 113, and Day 141) for IV administration. Appropriate aseptic technique will be used, and the study drug will be prepared according to the Pharmacy Manual for AK002.

The site's designated clinical staff will keep accurate and current accounting of the preparation and dose calculation of study drug for each patient, with source, quantities of study medication dispensed, used, and returned. All dosage calculations will be documented on the source documents. A study drug receipt, dispensation, and disposition log will be maintained by the pharmacist on the Investigational Drug Accountability Record. A study monitor will verify entries on these documents throughout the course of the study.

Specific instructions on administration are detailed in the Pharmacy Manual. In general, all doses i.e., 0.3 mg/ kg at Day 1, 1 mg/kg at Day 29 and Day 57, and either 1 mg/kg or 3 mg/kg (depending on UCT score) at Day 85, Day 113, and Day 141 will be given as an IV infusion over approximately 4 hours, following an observation period of 4 hours.

All dosages prescribed and dispensed to the patient and all dose changes during the study must be recorded on the appropriate eCRF.

Subjects in the CholU, UF, and CSU-XOLAIR® (omalizumab) failure cohorts who received all 6 infusions of AK002, were followed through Day 155, and demonstrated severe symptoms of urticaria following discontinuation of treatment will be eligible to receive extended dosing with up to 12 additional doses of AK002 (see [Appendix 2](#)).

For extended dosing, subjects must have a baseline (Day 1) UCT of  $\leq 5$  and a week 22 (Day 155) UCT of  $\geq 12$  (Complete Response). They must have a UCT of  $\leq 5$  between Day 155 and Day 309 (i.e., within 6 months from last dose).

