### **8.3.6 Permitted Study Drug Dose Adjustments and Interruptions**

AK002 dose adjustments are not permitted. The IV infusion may be interrupted, and/or the rate may be reduced by 50%, if a patient experiences an infusion-related reaction. The time the infusion is initiated/concluded (including any interruptions) will be documented in the eCRF. Infusion interruptions and infusion rate reductions should be documented when reporting any infusion-related reaction AEs. If dose is restarted after an interruption, the infusion must be completed within the 8-hour stability window. Administration will be discontinued if, in the opinion of the Investigator, an interrupted infusion cannot be restarted for safety reasons or if the infusion cannot be completed within the 8-hour stability window.

Administration will also be discontinued in any patient experiencing an SAE during the course of the infusion. A lower infusion rate in new subjects will be considered after assessment of safety results and discussion with the Medical Monitor.

Acetaminophen, antihistamines, and, if needed, a glucocorticoid (e.g., 125 mg methylprednisolone IV) may be administered to the patient if the patient experiences reactions that are considered mild to moderate (e.g., itching or a localized rash) at the Investigator's discretion. If a patient experiences signs or symptoms of anaphylaxis, the patient will be treated with standard of care, such as diphenhydramine, acetaminophen, methylprednisolone, epinephrine, and other supportive measures along with cessation of the infusion. As part of the anaphylaxis assessment, a sample of blood should be obtained for plasma histamine and tryptase level within 1 to 2 hours of the onset of the symptoms.

Any missed or altered study drug administrations must be recorded on the Dosage Administration Record eCRF in order to reconstruct an accurate dosing history for each patient.

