**Table 2      Prohibited Treatments**

Medication	Minimum Required Period without Medications
Omalizumab	within 2 months of Baseline
H2-antihistamines	7 days prior to Baseline
Routine (daily or every other day during 5 or more consecutive days) doses of systemic corticosteroids	14 days prior to Baseline
Routine (daily or every other day during 5 or more consecutive days) doses of systemic hydroxychloroquine	30 days prior to Baseline
Routine (daily or every other day during 5 or more consecutive days) doses of methotrexate, cyclosporine A, cyclophosphamide, tacrolimus and mycophenolate mofetil	4 weeks or 5 half-lives prior to Baseline
Intravenous immunoglobulin G	30 days prior to Baseline
Plasmapheresis	30 days prior to Baseline
Regular (daily or every other day) doxepin (oral)	14 days prior to Baseline
Inactive vaccination	30 days prior to Baseline
Live attenuated vaccine	30 days prior to Baseline
Leukotriene Antagonists	7 days

If the prohibited treatment was used during the study for any indication, the patient must discontinue use of the prohibited treatment if he/she wishes to continue in the study. If the patient received a live virus vaccination during the study, the patient must discontinue study treatment.

The list of prohibited medications is not considered all inclusive. Medication should be assessed for adherence to the indication and other inclusion/exclusion criteria.

The Investigator should instruct the patient to notify the study site about any new medications he/she takes subsequent to receiving the study drug. All medications and significant non-drug therapies (including physical therapy and blood transfusions) administered following initial study drug treatment, must be listed on the concomitant medications/significant non-drug therapies CRF.

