3.9.9 Prior, Concomitant, and Prohibited Medications

Prior medications and concomitant medications will be extracted from the Prior/Concomitant Medication CRF. Medications taken prior to Study Day 1 will be considered as prior medications and medications taken on or after Study Day 1 will be considered as concomitant medications. Prior and concomitant medications will be coded using WHO Drug Dictionary (WHODD March 2018 release) for Preferred Term (PT) and Anatomical Therapeutic Chemistry (ATC) classification.

Prohibited medications include, but are not limited to,

- Omalizumab
- H2-antihistamines
- Routine (daily or every other day during 5 or more consecutive days) doses of systemic corticosteroids
- Routine (daily or every other day during 5 or more consecutive days) doses of systemic hydroxychloroquine
- Routine (daily or every other day during 5 or more consecutive days) doses of methotrexate, cyclosporine A, cyclophosphamide, tacrolimus and mycophenolate mofetil
- Intravenous immunoglobulin G
- Plasmapheresis
- Regular (daily or every other day) doxepin (oral)
- Inactive vaccination
- Live attenuated vaccine
- Leukotriene Antagonists

4. Definitions

Table 4 Terminology and Definition

Terminology	Definition
Study Medication/Drug (SM)	AK002 administered by IV infusion.
Study Day	The first dose date (Day 1) is defined as the date on which a subject took the first dose of study medication (SM). Other study days are defined relative to Study Day 1. For visits prior to the first dose of the SM, Study Day is calculated as Visit Date – Day 1. For visits after the first dose, Study Day is calculated as Visit Date – Day 1 +1.
Enrolled	Subject who has signed informed consent, met all eligibility criteria at Screening, and having received the first dose of the study drug.
Completer for the Study	Subject who completes End of Study visit
Baseline	Baseline is defined as the non-missing value collected most recent to and before the time of the very first dose of the SM.
Prior Medication	Medication collected on the Prior/Concomitant Medication CRF, with start date prior to Study Day 1.
Concomitant Medication	Medication collected on the Prior/Concomitant Medication CRF, with end date on/after Study Day 1.
Treatment-emergent	Adverse events with onset date on or after the start of first study drug administration.

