11.1 Appendix A: Exclusion Criteria for the Per Protocol Populations

The following criteria will be used to further exclude subjects from the PP population:

- Subject received incomplete dose of study drug.
- Subject received prohibited medication that could potentially confound the efficacy outcome.

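### Depot, short-burst or infusion-reaction steroids are not clearly prohibited on study, and the SAP has no rule for UCT scores whose 4-week recall contains them

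*Protocol*

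**What the plan says.** **Entry.** Protocol 7.2.2, criterion 17, excludes "Intake of systemic corticosteroids (e.g., oral or depot) within 14 days prior to enrollment". It sets no minimum duration.

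**On study.** Protocol 8.3.10 applies Table 2 from Visit 1 onward. The steroid entry there is "Routine (daily or every other day during 5 or more consecutive days) doses of systemic corticosteroids". SAP 3.9.9 repeats that entry in its own list of prohibited medications.

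**Permitted or open use.**
- For mild to moderate reactions, Protocol 8.3.6 says that "if needed, a glucocorticoid (e.g., 125 mg methylprednisolone IV) may be administered to the patient".
- Protocol 8.3.5, on premedication after the first two infusions: "Any premedication for subsequent doses will be based on the Investigator's discretion". The only agents named for doses 1 and 2 are acetaminophen/paracetamol and cetirizine.
- Protocol 6.4, on flares: "Investigators will be instructed on acceptable treatments for worsening CU, which will allow subjects to continue on the study". The treatments are not listed.

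**Analysis.** The primary variable is change from baseline in UCT at Week 22, or at Week 10 for subjects enrolled under Amendment 2.1 (SAP 5.1 and 7.7.1). LOCF fills missing values. The primary analysis is repeated in the per-protocol set (SAP 7.7.1.1). The medication criterion in SAP Appendix A is "Subject received prohibited medication that could potentially confound the efficacy outcome".

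**The concern.** There is no control arm, so each subject's own baseline is the only comparator. A treatment that can suppress urticaria should then be defined alike on both sides of Day 1, or the analysis should say what happens to scores collected under it. The plan does neither for systemic steroids outside the five-day routine pattern.

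A steroid given for a flare or an infusion reaction in the weeks before the Week 22 visit can improve the score, and the plan would count that improvement as AK002 effect. The same UCT also defines CR, CMR and DC (SAP section 4), so the response rates are exposed too. The per-protocol repeat is where one would look for reassurance. Its medication criterion depends on the word prohibited, so it inherits the uncertainty about which steroids count.

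**Working it through.** The plan gives no figure to reproduce here: no hypothesis test, SD, steroid-use rate or steroid effect is stated. The check is a reading of the text plus simple arithmetic.

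**1. Definitions side by side**

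| Place | Systemic steroid covered | Minimum duration |
|---|---|---|
| Protocol 7.2.2, no. 17 (before entry) | any, oral or depot | none |
| Protocol Table 2 (from Visit 1) | routine daily or alternate-day dosing | 5 consecutive days |
| SAP 3.9.9 (analysis) | as Table 2 | 5 consecutive days |
| Protocol 8.3.6 (infusion reactions) | glucocorticoid permitted | not applicable |

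A single depot injection or a 4-day burst meets the first row but not the second or third.

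**2. Recall window of the primary UCT.** Recall is 4 weeks (Protocol 10.4.2).
- Week 22 is Day 155, and 155 − 28 = Day 127. Dose 6 on Day 141 falls 155 − 141 = 14 days before the visit. With ±2 days on both visits the gap is 10 to 18 days, always inside the window.
- Week 10, by the same day numbering, is 7 × 10 + 1 = Day 71 (compare 7 × 22 + 1 = 155). Its window opens at 71 − 28 = Day 43 and contains the Day 57 infusion.

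**3. Recall window of the baseline UCT.** Protocol 5.1 also uses a 4-week recall at baseline. Criterion 17 covers 14 of those 28 days. In the other 14 days only the Table 2 wording applies, so short use is not clearly barred there either. Such use would raise the baseline score and work against the drug. The asymmetry is therefore partial.

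**4. Tracing one case.** Take a depot injection on Day 135.
- It does not match the listed Table 2 pattern.
- The Week 22 UCT is observed, so LOCF does not act and the value enters the primary mean unchanged.
- Appendix A removes the subject only if someone decides that the injection counts as prohibited.
- If Week 22 were missing, LOCF could carry forward an earlier score that was itself obtained under steroids.

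**5. Size.** With 12 subjects per cohort (SAP 3.3), if k subjects each gain g points from steroids, the mean shifts by k × g / 12. Both k and g are assumptions.

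| k | g = 3 | g = 6 | g = 9 |
|---|---|---|---|
| 1 | 0.25 | 0.50 | 0.75 |
| 2 | 0.50 | 1.00 | 1.50 |
| 3 | 0.75 | 1.50 | 2.25 |
| 4 | 1.00 | 2.00 | 3.00 |

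Each subject wrongly counted as a responder adds 1/12 = 8.3 percentage points to the cohort rate; three add 25.0.

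**6. Chance that a cohort is touched.** 1 − (1 − p)^12 for an assumed rate p of steroid use in the window gives 21.5% at p = 2%, 46.0% at 5%, 71.8% at 10% and 93.1% at 20%.

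**The case against.** The strongest reply is that the documents leave room to catch this.
- The SAP list opens with "Prohibited medications include, but are not limited to". The text under Table 2 likewise says that the list is not exhaustive and sends the reader back to the eligibility criteria, one of which is criterion 17.
- Protocol 9.4 allows withdrawal when an exclusion criterion arises on study and threatens the integrity of the data.
- Protocol 13.1.3 and SAP 7.1.3 remove subjects with major violations from the per-protocol set before Appendix A is applied, and the deviation categories in SAP 7.3 are open-ended.
- SAP 7.6.2 tabulates all concomitant medication and lists it with study day, so steroid use would be visible.

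All of this stands. A reader might infer that a short burst is definitely allowed, or that the per-protocol repeat cannot detect it. The documents support neither. What remains is that each safeguard depends on judgement, exercised in an open-label study, and none states how an affected UCT is analysed.

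Two further points also stand. No section names a steroid as premedication, so that route is only a possibility left open by investigator discretion. And one infusion-reaction dose on Day 141 covers a small part of a 28-day recall; nothing in the documents shows that it moves the score.

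Finally, this is an exploratory pilot without hypothesis tests, and a randomized placebo-controlled study would be considered afterwards. That limits the consequences but does not remove the need for a rule, because the Week 22 change and response rates are its main efficacy results.

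**Conclusion.** The point holds in limited form. The entry criterion, Table 2, SAP 3.9.9 and Protocol 8.3.6 treat systemic steroids differently. Depot or short use is not clearly prohibited, and the plan has no prespecified handling for a primary UCT whose recall contains it. The primary analysis would keep such scores, and the per-protocol repeat need not remove them.

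The size is unknown and rests wholly on assumed k and g. With one or two affected subjects per cohort the shift is at most 1.5 points in the range shown. Reaching the 3-point MCID takes, for example, 4 of 12 subjects gaining 9 points each. A reader might infer a large bias that always favours AK002. The documents do not show that: they give no steroid-use rate, and half of the baseline recall has the same gap. It is worth correcting because the cohorts are small, there is no control arm, and the data needed are already being collected.

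**What to change.** **Reconcile the text.** The sponsor should align criterion 17, Table 2, Protocol 8.3.6 and SAP 3.9.9 on which systemic steroids count. Which rule is right is a clinical matter and is not judged here.

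**Add to the SAP before database lock:**
1. A flag for any UCT with systemic corticosteroid use of any duration, route or reason in the preceding 28 days. The source is the concomitant-medication CRF and the diary; the CholU and UF versions name cortisone, and the CSU version asks about other medications.
2. Use of this flag in Appendix A, and a report of flagged use by cohort.
3. Beside the as-observed Week 10/22 results, a sensitivity summary in which a flagged UCT counts as non-response for CR, CMR and DC and as zero change for the mean, and is not carried forward by LOCF. Because entry requires a UCT below 12, zero change and non-response agree for all three definitions.

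Replacing a flagged score with the last unflagged one is a tempting alternative but a poor one. If the steroid treated a flare, it can restore a better pre-flare score and favour AK002. The flag should also stay with steroids: extending it to every Table 2 class would mark vaccinations as confounders.

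**Cost.** SAP wording, one extra table set, a slightly smaller per-protocol set, and a conservative figure that may look less favourable.

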## **9. Discontinuation and Replacement of Subjects and Major Protocol Deviations**

### **9.1 Definition of Early Termination from the Study**

A patient who discontinues the study before completing the Follow-Up visit at Week 28 is considered to have terminated early. All subjects who discontinue the study prior to completing the final Follow-Up visit should return to the site 28 ( $\pm 2$ ) days after the last dose of study drug or prior to this if necessary. If early termination occurs more than 28 days after the last dose of study drug, then perform the Early Termination Visit as soon as possible.

### **9.2 Definition of Study Completion**

A patient who completes visits through the end of the Follow-Up visit at Week 28 will be recorded as having completed the study.

### **9.3 Early Discontinuation of Study Drug**

A patient may be discontinued from study treatment at any time if the patient, the Investigator, or the Sponsor feels that it is not in the patient's best interest to continue to participate in the study. The following is a list of possible reasons for study treatment discontinuation:

- Patient withdrawal of consent
- AE that, in the opinion of the Investigator, results in it being in the best interest of the patient to discontinue study treatment
- Protocol deviation requiring discontinuation of study treatment

If a patient is withdrawn from treatment due to an AE, the patient will be followed by the Investigator as noted in Section 9.4.

All subjects who discontinue study treatment should return to the site 28 ( $\pm 2$ ) days after the last dose of study drug for procedures listed under Post-Treatment Follow-Up.

All subjects are free to withdraw from participation at any time, for any reason, specified or unspecified, and without prejudice.

Reasonable attempts will be made by the Investigator to provide reasons for patient withdrawals. The reason for the patient's withdrawal from the study will be specified in the patient's source documents.

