## 9.4 Withdrawal of Subjects from Study

Participation of a patient will be discontinued in the event that:

- An AE or SAE that, in the judgment of the Investigator, requires withdrawal due to its nature, severity, or required treatment, regardless of the causal relationship to treatment
- Major protocol deviations as determined by the Medical Monitor, including significant non-compliance, or loss to follow-up
- Occurrence of an exclusion criterion which is clinically relevant and affects the patient's safety or integrity of the study data, if discontinuation is considered necessary by the Investigator and/or Medical Monitor
- Serum transaminases (ALT and/or AST)  $>3 \times$  ULN AND total bilirubin  $>2 \times$  ULN (confirmed by repeat testing) without an alternative explanation
- Elevation of ALT or AST  $>3 \times$  ULN (confirmed by repeat testing) with the appearance or worsening of symptoms felt by the Investigator to be potentially related to hepatic inflammation, such as fatigue, nausea, vomiting, right upper quadrant pain or tenderness, fever, rash, or eosinophilia
- Use of a non-permitted concomitant drugs and treatments, as defined in Section 8.3.10 as determined by the Medical Monitor.
- Withdrawal of the patient's consent
- Participation in any other trial during the duration of this trial as determined by the Medical Monitor.
- Loss of ability to freely provide consent through imprisonment or involuntarily incarceration for treatment of either a psychiatric or physical (e.g., infectious disease) illness
- Lack of efficacy
- Study terminated by sponsor
- Discretion of the Investigator

If a patient is withdrawn from treatment due to an AE, the patient will be followed and treated by the Investigator until resolved or stable.

Reasonable attempts will be made by the Investigator to provide reasons for patient withdrawals. The reason for the patient's withdrawal from the study will be specified in the patient's source documents.

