## **10. Visit Schedule and Assessments**

[Table 3](#) shows the schedule of assessments by study visit. Subjects should be seen for all visits on the designated day or as close to it as possible.

Subjects discontinuing the study drug before completing the 12-week treatment period, and those who prematurely withdraw from the study for any reason, should be scheduled for an early termination visit as soon as possible, at which time all of the assessments listed for the final visit will be performed.

Subjects who discontinue AK002 treatment also should return for the final assessments. If they refuse to return or are unable to do so, every effort should be made to contact them or a knowledgeable informant by telephone to determine the use of rescue medication and to complete the [REDACTED].

At a minimum, they will be contacted for safety evaluations during the 28 days following the last dose of AK002, including the final contact at the 28-day point. Documentation of attempts to contact the patient should be recorded in the patient record.

All data obtained from the assessments listed in Table 3 and described in detail in the protocol must be supported in the patient's source documentation.

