5.1 Primary Endpoint

- 1) The primary efficacy endpoint is the change in Urticaria Control Test (UCT) for each population (CSU-XN, CSU-XF, UF, and CholU). The UCT is a score for symptom control in chronic urticaria, from Day 1 (baseline) to Week 10 for subjects enrolled under Protocol Amendment 2.1 and Week 22 for all remaining subjects (i.e., those on study during Protocol Amendment 3). A change of the UCT score of 3 or more points is regarded as clinically relevant (minimal clinically important difference [MCID]). If Week 10 or Week 22 measures

are not available, they will be imputed with last observation carried forward method (LOCF). The data summary will include Week 10 and Week 22 derived from the available data and Week 10/LOCF and Week 22/LOCF derived from the available plus the imputed data.

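### Subjects who stop AK002 early are sent to an exit visit that falls before Week 22, and nothing asks for their UCT at the primary time point

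*Protocol*

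**What the plan says.** The primary endpoint is the change in UCT from Day 1 to Week 22 (Protocol 5.1). SAP 5.1 keeps Week 22 for most subjects and sets Week 10 for those enrolled under Amendment 2.1.

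For subjects who stop early, the protocol gives several instructions:

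- Section 9.3, on stopping study drug: a return visit 28 (±2) "days after the last dose of study drug for procedures listed under Post-Treatment Follow-Up".
- Section 10: subjects who stop drug early or leave the study "should be scheduled for an early termination visit as soon as possible", with the final-visit assessments. It adds, without a date: "Subjects who discontinue AK002 treatment also should return for the final assessments".
- Section 10, if they refuse or cannot come: "every effort should be made to contact them or a knowledgeable informant by telephone to determine the use of rescue medication", plus one redacted item. The floor, whose last contact falls 28 days after the final infusion, is: "At a minimum, they will be contacted for safety evaluations during the 28 days following the last dose of AK002, including the final contact".
- Section 9.1, on leaving the study: "A patient who discontinues the study before completing the Follow-Up visit at Week 28 is considered to have terminated early". The return visit is again set at 28 (±2) days after the last dose, or earlier if necessary. If the subject leaves later than that, it is held as soon as possible.
- Section 9.4 lists "Lack of efficacy" among the events that end participation.

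In SAP 5.1, a Week 10 or Week 22 UCT that is not available is to be "imputed with last observation carried forward method (LOCF"). The same section also reports both weeks from available data only. The MITT population needs one dose and one post-baseline UCT (SAP 7.1.1), so most early stoppers belong to it.

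**The concern.** Stopping the drug and leaving the study are different events, but the follow-up text treats them almost alike: one exit visit timed from the last dose. If that visit always comes before Week 22, the primary value of an early stopper is absent even when the subject is willing to give it.

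The SAP then offers two summaries, and neither measures the subject's Week 22 status. One substitutes an earlier score; the other drops the subject. With about 12 subjects per cohort, no control arm, and the primary summary given cohort by cohort (SAP 7.7.1), a few such subjects can visibly move a mean and its 95% confidence interval. There are no hypothesis tests (SAP 3.5), so what is at stake is the estimate and not a type I error rate.

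**Working it through.** The plan has no figure to reproduce here: it states no discontinuation rate, and the sample size rests on common practice (SAP 3.6). The check is calendar arithmetic followed by an illustration.

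**Inputs.** Dosing on Days 1, 29, 57, 85, 113 and 141 (Protocol 6.1). Return visit at last dose + 28 (±2) days (Protocol 9.3). Week 22 at Day 155 (±2) (Protocol Table 3). UCT recall of 4 weeks (Protocol 10.4.2). About 12 subjects per cohort (SAP 3.3).

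**Timetable.** Day 141 + 14 = Day 155 (Week 22) and Day 141 + 56 = Day 197 (Week 28), so the scheduled days agree with each other.

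**Exit visit against Week 22.** Exit day = dose day + 28; gap = 155 − exit day.

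| Last dose | Dose day | Exit day (±2) | Days before Day 155 | Last dose to Day 155 (days) |
|---|---|---|---|---|
| 1 | 1 | 29 | 126 | 154 |
| 2 | 29 | 57 | 98 | 126 |
| 3 | 57 | 85 | 70 | 98 |
| 4 | 85 | 113 | 42 | 70 |
| 5 | 113 | 141 | 14 | 42 |
| 6 | 141 | 169 | none (14 after) | 14 |

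The latest exit after Dose 5 is 113 + 28 + 2 = Day 143. If Dose 5 is itself 2 days late, it is Day 145. The Week 22 window opens on 155 − 2 = Day 153. Nobody who stops before Dose 6 and follows 9.3 has a Week 22 UCT. A subject who receives Dose 6 is not affected.

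**Amendment 2.1 subjects.** Week 10 is Day 10 × 7 + 1 = 71. Their dosing days are not given. Assuming Days 1, 29 and 57 fits the SAP 3.1 statement that Week 10 is 2 weeks after the last dose (57 + 14 = 71). Stopping after dose 1 or 2 then puts the exit on Day 29 or 57, which is 42 or 14 days too early.

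**Which score is carried.** The End of Study/Early Termination column of Table 3 includes the UCT, so the carried value is probably the exit UCT. Taken 28 days after the last dose, its 4-week recall covers the interval just after that dose.

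**Size, with assumed values.** Shift in cohort mean = k × c / n, where k is the number of subjects carried forward, c is the carried change minus the true Week 22 change, and n = 12.

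| k | c = 3 | c = 6 | c = 9 |
|---|---|---|---|
| 1 | 0.25 | 0.50 | 0.75 |
| 2 | 0.50 | 1.00 | 1.50 |

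If c = 0 the shift is nil. If c is negative, benefit is understated. Falls of this order are contemplated by the protocol: extended dosing (6.1.4) is for subjects who go from UCT of at least 12 at Week 22 to 5 or less, a loss of at least 12 − 5 = 7 points. That is an entry criterion, not a rate. If the carried score also fed the UCT response proportions, which SAP 5.2 does not state, each misclassified subject would move a cohort rate by 1/12 = 8.3 percentage points.

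**How many values.** Under an assumed 5% to 20% stopping early, 0.6 to 2.4 subjects per cohort of 12, or 2.4 to 9.6 of 48.

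**The case against.** **Later follow-up is not forbidden.** Section 9.3 does not say that scheduled visits end, Section 10 presents the 28-day contact as a floor, and stopping drug and leaving the study have separate sections. A reader might infer that the protocol deliberately excludes a Week 22 UCT; the text does not go that far. It is silent and inconsistent. But no sentence fixes a UCT at the primary time point. The undated return for final assessments does not do so. A leaver seen late under 9.1 could meet the Week 22 window only by chance.

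**The direction of bias is not fixed.** A reader might infer that LOCF always credits early stoppers with benefit they have lost. The documents do not support that. A subject who stops for lack of effect would carry a poor score. Overstatement needs a subject who responded, stopped for another reason and then relapsed. Nor is the carried score necessarily an on-treatment one, since it is probably the exit UCT. The completers' own Week 22 value, 2 weeks after Dose 6 with 4-week recall, largely reflects time on drug. This objection stands.

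**LOCF is not the only summary.** Also true, and readers can compare the two. The available-data version does not recover the missing values.

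**A score up to 154 days after the last dose answers a different question, and other therapy may have begun.** This is fair. It is a reason to flag such subjects and to keep the LOCF summary, not to leave the value uncollected.

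**The telephone contact in Section 10 is not a ready substitute.** It may reach an informant, who cannot answer a patient-reported questionnaire, and it is not tied to Week 22. This stands and shapes the fix.

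**Conclusion.** The concern holds as a gap in data collection. A subject who stops before Dose 6 and follows the written schedule exits 14 to 126 days before Day 155 without a Week 22 UCT. SAP 5.1 then either carries an earlier score forward or omits the subject.

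The size and direction of any resulting bias cannot be determined from the documents. The range of 0.25 to 1.5 points assumes one or two affected subjects in a cohort of 12, each carried 3 to 9 points too high. With no such subject it is zero. A reader might set that shift against the 3-point minimal clinically important difference, but the protocol (10.4.2) and SAP (Section 4) use that threshold for an individual's response, not for a cohort mean. In an exploratory study without tests, this is a change that should be made, not one that invalidates the plan.

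**What to change.** **Protocol 9.1, 9.3, 9.4 and 10.** Reconcile the wording: the 28-day return, the immediate early termination visit, the undated final assessments, and the 12-week treatment period in Section 10 against dosing to Day 141. State separately what follows from stopping AK002 and from leaving the study. Ask subjects who stop drug for any reason, including lack of efficacy, and have not withdrawn consent to complete the UCT at Week 22 (Week 10 for Amendment 2.1 subjects). This can be done at site or by telephone with the patient in person, not an informant. It concerns data collection only and changes no dose or treatment rule.

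**SAP 5.1.** Use that observed value in the primary summary. Flag subjects who began other urticaria therapy after stopping. Keep the LOCF summary as a sensitivity analysis. LOCF is then needed only where the primary-time UCT was not obtained, chiefly after consent withdrawal or loss to follow-up.

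**Cost.** One four-item questionnaire or call per discontinuer and a small amendment. The drawback is that some off-drug values will reflect other therapy, which is why the flag is needed.
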